Compliance with the supplement will be assessed at the final visit. Participants will be instructed to bring back all study product bottles containing any remaining capsules. The remaining capsules will be counted and recorded by a member of the study team. Compliance with the supplement will be reported as a percentage based on calculating the amount of pills consumed in comparison to the amount expected according to instructions.

Statistical Analysis

Since the pilot study is not powered to demonstrate efficacy, analysis of the pilot study results will be strictly descriptive. Baseline demographics and outcome measures will be summarized by group as means and confidence intervals, medians and interquartile ranges, or percentages and confidence intervals as appropriate. Process evaluation will be described both quantitatively (percent screened positive for inclusion, percent of eligible patients who consent to participate, percent with significant protocol violations, etc.) and qualitatively (e.g., reasons for failing inclusion criteria, reasons for refusing to participate, participant impressions of the intervention, etc.). All participants will be analyzed in the group to which they were randomized. Missing data will be carefully documented to inform the design of the larger trial. Participants who complete the treatment but do not report a satisfaction level will be treated as 'unsatisfied.' No interim analysis will be undertaken. The study will be considered feasible if 50 participants are recruited within two years, and participants in the intervention group take at least 60% of the study product and attend at least 60% of the diet counselling sessions. The study will be considered acceptable if at least 70% of participants report that they were satisfied with the intervention. The statistical analysis plan for the full-scale trial is included in Supplemental file 5.

Data management

The collection and storage of data will be done according to Good Clinical Practice Guidelines. All study staff involved in the collection or entry of data will be trained by the trial coordinator and will complete

ethical conduct of research training (Tri-Council Policy Statement: Ethical Conduct of Research Involving Humans 2). Data from potential and enrolled participants will be stored in the secure platform, Research Electronic Data Capture (REDCap) and a password protected database on a secure server managed by the Canadian College of Naturopathic Medicine. Data collected at each study visit will be captured using an electronic case report form which will be entered into the database. Questionnaire completion will be done by the study participants through REDCap. Laboratory data will be entered into the database and double checked for accuracy by a team member blind to participant allocation. An audit of the data will be completed by a senior member of the research team who is not involved in data collection after 10 participants are enrolled or three months of time, whichever comes first. All information obtained during the trial will be kept in a locked cabinet or on a password protected computer and destroyed (deleted or shredded) after 15 years.

Access to Data and Dissemination

All personal health information will be kept confidential and only accessed by the research team, unless required by law. This includes audit by CCNM Research Ethics Board or Health Canada Natural and Non-prescription Health Products Directorate. All data will be maintained on password protected, secure servers or locked filing cabinets for the required length of time. Following this time, data will be destroyed securely by deleting the digital files or shredding paper documents. No identifying information from any participant will be used in the dissemination of study results. Dissemination of the study findings will occur through publication. Study participants will have the option to be notified of the study findings.

Discussion

Given the increasing attention to the importance of nutrition in mental wellbeing being communicated to the general public by the popular media, we expect that participants will be interested in the trial and

that it will be feasible and acceptable. Given the abundance of observational data suggesting an important role of food choices in the development and progression of psychiatric disorders, in conjunction with the positive findings from recent intervention studies in depression, we expect that participation in the intervention will result in improvement of anxiety symptoms.

At this present time, attention to the role of diet and lifestyle in guidelines for the prevention and treatment of psychiatric disorders is significantly lacking. This trial will build the foundation for larger, adequately powered studies which will add to the expanding evidence base attesting to the importance of nutrition in mental health care. This type of evidence is creating a rationale for the inclusion of nutrition professionals in mental health care teams and use of dietary counselling in the treatment of mental illness. It will open the door to shifting policy and increasing access. Nutrition interventions can be low in risk, acceptable to patients, cost effective(10) and may have additional benefits to overall health. Nutritional counselling may be a way for nutrition professionals to contribute to meeting the needs of a patient population who report that presently available treatment options are often not accessible, effective, or tolerable, resulting in a decreased personal and social burden of GAD(4).

List of Abbreviations:

GAD: generalized anxiety disorder, EPA: Eicosapentaenoic acid, DHA: Docosahexaenoic acid, REDCap: Research Electronic Data Capture, EASe-GAD: Eating and Supplementation for Generalized Anxiety Disorder study, PROMIS: Patient Reported Outcomes Measurement Information System

Declarations

Ethics approval and consent to participate: The study has been reviewed by the Research Ethics Board of the Canadian College of Naturopathic Medicine (CCNMREB040.[name]). All participants will provide written informed consent. All research will be conducted in accordance with the Declaration of Helsinki and all other relevant guidelines and regulations.

Consent for publication: Not applicable

Availability of data and materials: The datasets used and/or analysed during the current study available from the corresponding author on reasonable request.

Funding: This study received funding or gifts in kind from Ekhagastiftelsen, AquaOmega, Mitacs Accelerate, Lipid Analytical Laboratories and Sobeys Inc. Trial funders had no role in the design of the study. A research team member from Lipid Analytical will complete the omega-3 analysis for blinded samples and assist with interpretation of blinded data. The other funders will have no role in the interpretation of finding. The funders will have no role in writing the manuscript.

Competing Interests: The authors report no conflicts of interest.

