2. Primary diagnosis of generalized anxiety disorder based on a clinical interview with a psychiatrist using the Diagnostic and Statistical Manual of Mental Disorders (DSM-5) criteria.
3. Moderate to severe anxiety as defined as a Beck Anxiety Inventory score of 22 or higher.
4. Low quality diet as defined as a score of 8.5 or less on the MEDI-LITE tool.
5. All psychiatric medication, psychotherapy, and natural health products stable for the past four weeks.
6. Established therapeutic relationship with a family doctor, psychiatrist, or clinical psychologist as their primary source of mental health care.
7. Ability to swallow capsules.
8. Ability to read in English and provide informed consent.

Exclusion Criteria:

1. Currently meets DSM-5 criteria for obsessive-compulsive disorder, bipolar disorder, a psychotic disorder, an eating disorder, or substance use disorder based on clinical interview with a psychiatrist.
2. Current high level of suicidality assessed by trial psychiatrist using the Columbia Suicide Severity Scale.
3. Starting or changing the dose of a psychiatric medication, psychotherapy, or natural health products in the past four weeks.
4. Severe food allergies, intolerances or aversions that would prevent the individual from modifying their diet (includes aversion to bovine gelatin which is a component of the fish oil supplement).

5. Current participation in a program, research study or treatment plan involving diet or lifestyle modification.
6. Baseline Omega Score of >5% (suggesting adequacy of omega-3 fatty acids).
7. Supplementation of greater than 4000IU of vitamin D daily for at least one month in the previous six months.
8. Allergy to fish or any of the non-medicinal ingredients in the study product.

Participants who are assigned to the waitlist control, who do not meet one or more of the criteria at the time of starting the intervention will still be permitted to participate. This data will be included in the analysis. If a participant begins a new medication or psychotherapy, or adjusts the dosage, during the waitlist period, this new treatment must be stable for four weeks prior to beginning the treatment phase of the study, even if this requires extending the waitlist period by up to four weeks.

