Participants with co-morbid depression will be eligible to participate in the intervention because of the high level of comorbidity with GAD(34). The criterion related to recent high dose vitamin D supplementation is included to identify potential participants who would exceed the maximum recommended daily allowance of vitamin D if they began taking the study product. Initially, this exclusion criterion was “Supplementation of greater than 1700IU of vitamin D daily [...]”; however, early results from screening identified a high number of interested individuals who were ineligible because of this criterion and an amendment was made to make the study more inclusive without compromising on participant safety. In order to ensure that participants have access to adequate care, should they experience a serious worsening of their psychiatric illness during the study period, an established therapeutic relationship with a mental health professional is required.

Sample Size and Recruitment Plan

Because of the pilot nature of the present trial, a formal sample size calculation was not completed. No intervention study has attempted to deliver a dietary intervention to participants with GAD and thus, the expected effect is unclear. The results of this pilot trial will inform the sample size calculation for a full-scale trial.

Participants will be recruited through multiple strategies. Letters will be mailed to local mental health service providers including psychiatrists, counsellors, psychotherapists, and psychologists. The clinicians will be provided with a poster to display in their office and fliers to distribute directly to clients.

Additional recruitment strategies will include online advertising through Facebook and other social media sites. This will include posts in existing, local anxiety/mental health groups and paid advertisements. If needed, newspaper advertisements may be used.

Pre-study Screening, Randomization and Baseline Evaluation

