Interested participants who contact the study will complete a virtual screening visit. A member of the research team will administer the MEDI-LITE Score, and the Beck Anxiety Inventory and review the additional inclusion and exclusion criteria by phone or secure video call. If the participant meets these criteria, they will complete the clinical interview and Columbia Suicide Severity Scale with the trial psychiatrist by secure video platform. Following the completion of a verbal consent process, the participant will be mailed a kit for collecting a blood spot sample at home and will return the sample by mail for analysis of baseline omega-3 status.

Individuals who meet all study inclusion criteria will be contacted and invited to enroll in the study. There is no predetermined time between screening and baseline; as soon as all screening requirements are complete, enrollment and baseline data collection can begin. The baseline activities and data collection will take place through a combination of virtual and in-person activities. In an enrollment video call with the study coordinator, participants will complete the informed consent process by reviewing the informed consent form and asking questions. Following enrollment, baseline data collection will involve the completion of several questionnaires through a secure online platform (Supplemental File 2). If the participant does not have access to an internet enabled device, they will be mailed a paper copy of the baseline questionnaires. Baseline assessment will also include the provision of a fasting blood sample. Following baseline data collection, participants will attend an in-person study visit. At this time, baseline height and weight will be measured, and the participants will be randomized. Randomization will be completed by the trial coordinator using a computer-generated internet-based

randomization service provider using random permuted blocks. Following assignment, the trial coordinator, intervention deliverer, and participants will be aware of allocation. Outcome assessors will be blind to allocation when measuring height and weight. Measurement of the omega-3 samples and interpretation of the data will be completed by a research team member who is blind to allocation. Data analysts will be blind to allocation; they will be provided with data from two groups of participants labelled group 1 and 2.

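### The eligibility waiver for waitlisted participants excepts no safety exclusion, and no re-check of allergy, vitamin D intake or suicidality is stated before their first dose, 86 to 114 days after allocation

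*Combined protocol and SAP*

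**What the plan says.** The waiver follows directly after the exclusion list in Participants Eligibility: waitlisted participants "who do not meet one or more of the criteria at the time of starting the intervention will still be permitted to participate". Their data stay in the analysis.

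One condition comes with it. "If a participant begins a new medication or psychotherapy, or adjusts the dosage, during the waitlist period", the new treatment must be stable for four weeks before the intervention starts, and the wait may be lengthened by up to four weeks to allow this. Exclusion 3 is wider, since it also names natural health products: "Starting or changing the dose of a psychiatric medication, psychotherapy, or natural health products in the past four weeks".

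The exclusions that matter most here are:

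- Exclusion 2: "Current high level of suicidality assessed by trial psychiatrist using the Columbia Suicide Severity Scale".
- Exclusion 7: more than 4000 IU of vitamin D daily for at least a month in the last six. The rationale is that such people "would exceed the maximum recommended daily allowance of vitamin D if they began taking the study product".
- Exclusion 8: "Allergy to fish or any of the non-medicinal ingredients in the study product".

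Under Pre-study Screening, Randomization and Baseline Evaluation, people who pass the first review go to the psychiatrist: "they will complete the clinical interview and Columbia Suicide Severity Scale with the trial psychiatrist by secure video platform". The same section adds: "There is no predetermined time between screening and baseline".

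**The concern.** Some entry criteria choose suitable candidates: the Beck score, the MEDI-LITE score, the Omega Score. Waiving these for someone who has already been randomised and has waited is sensible, because scores drift and the randomised group should be kept whole. Other criteria guard against harm from the product, or against starting a trial intervention in a psychiatric crisis. They matter at the moment of starting, and the vitamin D rationale says as much. The waiver treats both kinds alike.

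At stake is patient safety. On the wording, a waitlisted participant who develops a fish allergy, or begins high-dose vitamin D, during the wait may be given the product without anyone being required to ask. For suicidality the question is narrower: whether a deterioration would be noticed before the first dose or only after it.

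**Working it through.** **1. Age of the checks at first dose.** Supplemental File 2 gives allocation on Day 0, end of wait on Day 85, and the first session on Day 1 (immediate start) or Day 86 (waitlist). Participants Eligibility gives the extension, up to four weeks (28 days). I assume the product is started at the first session.

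- Waitlist arm: 86 − 0 = 86 days; 86/7 = 12.3 weeks.
- With the extension: 86 + 28 = 114 days; 114/7 = 16.3 weeks.
- Excess over the immediate-start arm: 86 − 1 = 85 days, or 114 − 1 = 113 days.
- The time from screening to baseline has no set limit and is added in both arms.

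**2. What is checked, and when.**

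| Item | Stated check | Later safeguard | Stated re-check before waitlist first dose |
|---|---|---|---|
| Fish or ingredient allergy (8) | Criteria review at screening | Diphenhydramine supplied; withdrawal after a reaction | None |
| Vitamin D intake (7) | Screening, with step-down to 1700 IU for those on 1701 to 4000 IU | Natural health product query at follow-up visits; changes recorded, no action threshold | None |
| High suicidality (2) | Columbia scale at screening | Worsening question at follow-up visits, ASQ if ideation is reported, withdrawal rule | None certain (see step 4) |
| Psychosis | Psychiatrist interview at screening | Same question; referral if symptoms are reported; withdrawal rule | None certain (see step 4) |

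The withdrawal rule for serum 25-hydroxy-vitamin-D above 120 nmol/L refers to the baseline level, and no repeat is stated.

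**3. End-of-wait assessment.** Items marked for the waitlist arm in Supplemental File 2 are MEDI-LITE, Beck Anxiety Inventory, Omega Score, Mindful Eating Questionnaire, PROMIS-29, physical activity, self-efficacy, height and weight, and a laboratory panel. None is described as a check of allergy, vitamin D intake, suicidality or psychosis. The assessment exists but does not serve this purpose.

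**4. Does the first waitlist session count as a follow-up visit?** The worsening question (Safety and Criteria for Withdrawal) and the natural health product query (Concomitant Therapies) are both asked at follow-up visits.

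- If Day 86 counts, both are asked on the day of starting. The supplement answer still triggers no stated action.
- If it does not, as the split between first and follow-up sessions in Table 2 suggests, both are first asked at the next session, Day 100: 100 − 86 = 14 days after the product is started.

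The text does not settle which reading is meant.

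**5. Vitamin D illustration.** The product supplies 800 IU. Concomitant Therapies aims for at most 1700 + 800 = 2500 IU in those who step down. Someone who began more than 4000 IU during the wait would take more than 4000 + 800 = 4800 IU. The wait is long enough for a new month of such use. The four-week stability condition would not catch it, because it covers medication and psychotherapy only. The documents give no figure for the maximum allowance, so I compute no excess over it.

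**6. Who is affected.** 25 of 50 participants. The documents give no rate at which people newly meet one of these exclusions, so no expected count is offered.

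**The case against.** The strongest reply is that the waiver does not stand alone. The withdrawal rule for severe suicidal ideation or psychosis is not limited by arm or period. Participants are told to contact the coordinator if their health seriously worsens, and each must have an established mental health provider. Supplement use and mental health are asked about at follow-up visits, and for a waitlisted participant the Day 86 contact can fairly be called a visit after baseline. Participants are encouraged to keep other treatments unchanged, and the first session includes an inquiry about food aversions.

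Much of this stands. A reader might infer that every safety exclusion is checked only at screening or baseline, or that the protocol knowingly lets an acutely suicidal participant start. The documents support neither: suicidality, psychosis and supplement use are all asked about again, and the withdrawal rule overrides the waiver in severe cases. For suicidality and psychosis, only the timing of detection remains open.

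A reader might also count exclusion 1 and the allergy part of exclusion 4 as safety criteria. The protocol does not say so. Exclusion 4 is framed around being able to change one's diet, and most of the diagnoses in exclusion 1 carry no stated safety reason.

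The reply does not reach allergy, where nothing is asked again and the remedy follows the reaction. Nor does it reach vitamin D, where an answer may be recorded but no action follows.

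**Conclusion.** The point holds within these limits. The waiver is written as a rule, it excepts no safety exclusion, and the plan states no re-check of exclusions 7 and 8 before a first dose that comes 12.3 to 16.3 weeks after allocation. For exclusion 2 and for psychosis, the protection exists, but the step that would trigger it may come up to one session late.

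Severity is modest. The primary objective (feasibility and acceptability), the secondary objectives and the descriptive analysis are untouched, and investigators may well act sensibly whatever the wording. The conclusion rests on the waiver being followed as written and on the product being started at the first session. It does not depend on any assumed event rate.

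**What to change.** 1. Keep the waiver for non-safety criteria such as the Beck Anxiety Inventory, MEDI-LITE and Omega Score. Add that exclusions 2, 7 and 8, and the withdrawal rules for severe suicidal ideation and psychosis, still bar product start. Participants held back remain in the analysis as randomised, in line with Statistical Analysis.
2. At the existing end-of-wait assessment, before product is dispensed, ask again about:
   - fish and ingredient allergy;
   - vitamin D intake, applying the existing reduction to 1700 IU to anyone on 1701 to 4000 IU;
   - worsening mental health, suicidal ideation and symptoms of psychosis, using the existing ASQ and psychiatrist referral path.

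A repeat psychiatrist interview for everyone is not needed. For that reason the bar should not extend to all exclusion 1 diagnoses, which could not be enforced without one.

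The cost is one or two sentences of protocol text and a few questions, with no new visit or instrument. A few waitlisted participants may not start the product. Each is 1/25 = 4% of the arm, or 1/50 = 2% of the trial, and should be reported as non-uptake with the reason.
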